4.7.2.3 Sensitivity Analyses

To assess the treatment effect in ALSFRS-R total score, the following sensitivity analyses will be performed using similar approaches as described in main analysis:

- ALSFRS-R total score comparison between PS matched (based on other caliper widths if available) Trehalose group and historical control group, including PS matched ID as random effect
- ALSFRS-R total score comparison between PS stratification-based Trehalose group and historical control group, including PS stratification-built strata as fixed effect

4.7.2.4 Supplementary Analyses

The following analyses will also be performed for the participants in PPS, using the same approaches as described above.

- ALSFRS-R total score summary for EAP study by treatment cohort and overall
- ALSFRS-R total score comparison between PS matched (based on the pre-specified caliper width for main analysis) Trehalose group and historical control group
- ALSFRS-R total score comparison between PS stratification-based Trehalose group and historical control group

In addition, an analysis of the total ALSFRS-R score will be performed using a general linear mixed effects model to compare the rate of decrease (ie, slope) of total ALSFRS-R scores over the 24-week treatment period between the PS matched (based on the pre-specified caliper width for main analysis) Trehalose and historical control, and between the PS stratification based Trehalose and historical control, respectively, for both FAS and PPS.

The model will fit a random intercept and slope for each participant and will include fixed effects for treatment group, bulbar onset (Yes/No), visit, and treatment by visit interaction. For comparison between the PS matched Trehalose and historical control, PS matched ID will be included as random effect; for comparison between PS stratification-based Trehalose and historical control, the PS stratification-built strata will be included as fixed effect.

An unstructured covariance structure will be used to model the within-participant errors. Visit will be expressed in weeks as a continuous variable and will include all scheduled visits including baseline as Week 0 (i.e., Week 0, Week 3, Week 12, Week 24). Missing values will not be imputed.

Estimates of the slope will be presented by the treatment group along with corresponding 95% CIs. The estimate of the difference between slopes (Trehalose vs. historical control) and the 95% CI of the difference between slopes will be presented. The null hypothesis of no difference in slopes between the treatment groups will be determined by testing the significance of the treatment by visit interaction term.

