4.7.2.2 Main Analytical Approach

For participants in FAS, the ALSFRS-R total score as well as the change from baseline will be summarized descriptively at scheduled visits (Baseline, Week 3, Week 12 and Week 24) by treatment group. The linear mixed-effects model for repeated measures (MMRM) will be used to calculate the least square mean for each treatment group, and the treatment difference between PS matched (based on the pre-specified caliper width for main analysis) Trehalose group vs. historical control group.

The MMRM model will include the ALSFRS-R total score change from baseline at scheduled post-baseline visits as the dependent variable, with fixed effects for treatment, bulbar onset (Yes/No) and baseline value, visit (as categorical variable), treatment-by-visit interaction, and baseline value-by-visit interaction, with visit as the repeating factor, participant as a random effect. PS matched ID will also be included as a random effect for comparison between Trehalose group vs. historical control group.

The MMRM model will use restricted maximum likelihood (REML) to estimate least squares means and treatment differences. An unstructured covariance matrix will be used to model within-participant errors. Data

from all scheduled visits over the treatment period will be used to fit the model. Missing data will not be imputed.

If the computational algorithm fails to converge, the following structures will be executed in the order specified until convergence is achieved: Toeplitz with heterogeneity (TOEPH), autoregressive with heterogeneity (ARH(1)), compound symmetry with heterogeneous variances (CSH), autoregressive (AR(1)), Toeplitz (TOEP), and compound symmetry without heterogeneous variances (CS).

At the post-baseline visits of Week 3, Week 12 and Week 24, the least square mean and standard error (SE), as well as 2-sided 95% CI for each treatment group will be provided. The difference (SE) and 95% CI, p-value between PS matched Trehalose group and historical control group will be summarized.

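### The PS-stratified ALSFRS-R slope model enters the PS strata as a main effect only, so its slope comparison is unadjusted; the PS-stratified MMRM adjusts Week 24 incompletely

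*SAP*

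**What the plan says.** SAP 4.2.4 cuts the trehalose participants and the eligible historical controls into strata at the PS quintiles of the treated. Strata lacking either group are dropped. The strata are then to be used in estimating the overall treatment difference. Controls in the strata are neither matched nor weighted.

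- **Slope model (4.7.2.4).** Each participant has a random intercept and slope, and the model "will include fixed effects for treatment group, bulbar onset (Yes/No), visit, and treatment by visit interaction". Visit is continuous in weeks ("i.e., Week 0, Week 3, Week 12, Week 24"). The strata come in by one clause, for the PS-stratified comparison: "the PS stratification-built strata will be included as fixed effect". The slope comparison is made by "testing the significance of the treatment by visit interaction term".
- **MMRM (4.7.2.3).** The PS-stratified version follows the main MMRM, "including PS stratification-built strata as fixed effect". The main MMRM (4.7.2.2) names the interactions it wants: "treatment-by-visit interaction, and baseline value-by-visit interaction, with visit as the repeating factor".

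Neither model lists a strata-by-visit term. Because 4.7.2.2 spells out its interactions, the natural reading of both later sections is a main effect only.

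**The concern.** PS stratification adjusts an estimate only if the strata enter the part of the model that carries the estimate. In the slope model that part is the time coefficient, and the strata are absent from it. Several PS covariates in 4.2.2 plausibly predict rate of decline: pre-baseline ALSFRS-R slope, time since onset and diagnosis, and % predicted VC. Cohort 1 consists of people who do not qualify for accessible trials, so a prognostic difference from historical controls is a real possibility.

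A reader comparing the stratified slope result with the matched one would take agreement or disagreement as evidence about robustness to the PS method. In fact the comparison would be matched against unadjusted. SAP Section 1 notes that the results might go into a regulatory submission, so the label matters.

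**Working it through.** The documents give no sample size, power or bias figure for the ALSFRS-R comparison, so there is no plan figure to reproduce.

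**1. Slope model, complete data.** Reduce each participant to a fitted intercept A and slope B. With common visit times, (A, B) has the same 2×2 covariance Ω for everyone.

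- Regressors for A: x = (1, treatment, bulbar onset, strata).
- Regressors for B: g = (1, treatment).

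Factor the likelihood as f(B)·f(A given B). The conditional mean of A is x′α + ω(B − g′γ), with ω = Ω12/Ω22. Every column of g is also in x, so x′α − ωg′γ is just x′ times a free vector. That factor carries no information on γ. Hence γ is estimated by regressing B on g alone, and the treatment-by-visit coefficient is the mean trehalose slope minus the mean control slope.

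If p_k and q_k are the shares of trehalose and control participants in stratum k, and β_k is the stratum's mean slope, the estimate carries the whole confounding term Σ(p_k − q_k)β_k. Bulbar onset, also a main effect only, has the same limit.

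**2. Numerical check of step 1.**

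- Complete data: estimates with and without strata differed by less than 1e-15 by GLS with known covariance. This also held for an arbitrary unstructured covariance, so the unstructured error matrix in 4.7.2.4 does not help.
- About 21% dropout (missing at random): ratio of the two estimates 1.000-1.001. The widest gap in any run was with 25% dropout: −0.202 without strata, −0.205 with.
- Controls on sparser visit schedules (for example Weeks 0, 12 and 24): equal to three decimals.

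**3. MMRM.** Suppose stratum effects grow linearly, β_k·t. The model fits one constant per stratum, a GLS-weighted average over t = 3, 12, 24. Let r = (between-participant slope SD / residual SD)². The shared baseline error does not alter the weights.

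- Σt = 3 + 12 + 24 = 39; Σt² = 9 + 144 + 576 = 729.
- Weights are proportional to 1 − 39r·t/(1 + 729r).
- Weighted mean time = 39/(3 + 3·729r − 39²r) = 39/(3 + 666r) = 13/(1 + 222r).
- Share of Week 24 confounding removed = [13/(1 + 222r)]/24. At Week 3, the adjustment made divided by that needed = [13/(1 + 222r)]/3.

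The SDs are assumptions; the documents give none.

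| Slope SD (points/week) | Residual SD (points) | r | Removed at Week 24 | Remaining | Week 3 made/needed |
|---|---|---|---|---|---|
| 0.10 | 2.5 | 0.0016 | 40% | 60% | 3.20 |
| 0.15 | 1.5 | 0.01 | 17% | 83% | 1.35 |
| 0.25 | 1.0 | 0.0625 | 4% | 96% | 0.29 |
| 0 (limit) | any | 0 | 54% | 46% | 4.33 |

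So the constant term under-corrects Week 24 and can over-correct Week 3.

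**4. Route of confounding.** The MMRM's baseline value-by-visit term already acts on confounding through baseline ALSFRS-R. In large null simulations with confounding only by that route, the crude Week 24 bias of 1.01 points became about −0.12 under the planned model. With an even mix of baseline score and progression rate, 0.132/0.267 = 49% remained. The slope model has no such term: with confounding only through baseline score its bias was 0.185 points/month with or without strata.

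**5. Effect of adding strata-by-visit.** Illustration with no true effect: 70 treated, 300 controls (pool size, variances and strength of confounding assumed), 10,039 replicates.

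| Model | Mean estimate, as planned | Mean, with strata-by-visit | Rejection at nominal 5%, as planned | Rejection, with strata-by-visit |
|---|---|---|---|---|
| Slope (points/month) | 0.202 (no strata: 0.202) | 0.035 | 48% | 5.0% |
| MMRM Week 24 (points) | 0.997 | 0.196 | 38% | 5.1% |

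Across the larger simulations, strata-by-visit left 1-31% of the slope bias and 3-32% of the crude Week 24 bias, so five strata do not remove everything.

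**The case against.** The SAP (Section 2) plans no formal hypothesis testing, calls the analyses descriptive and treats p-values as exploratory. The main efficacy comparison is on the matched groups (4.2.3), where balance comes from the matching. The PS-stratified ALSFRS-R models are listed as sensitivity and supplementary analyses, beside matched analyses at other caliper widths and repeats in the PPS. All of this stands and limits the weight of the point. A reader might infer that the main check on the matched result has failed; the SAP gives the stratified analysis no such role.

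A reader might also infer that the stratified MMRM is mostly unadjusted in general. That is too strong. Baseline value-by-visit already covers one PS covariate, and the remaining share depends on assumed variances and on the route of confounding.

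Bulbar onset-by-visit is not needed to repair the fault. Bulbar onset is already in the PS, and the SAP dropped it as a stratification factor from the matched survival analysis for that reason.

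None of this rescues the slope model. SAP 4.2.4 calls the strata a stratification factor, but 4.7.2.3 and 4.7.2.4 both specify a fixed effect, and that cannot move treatment by visit.

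**Conclusion.** The point holds for the slope model without assumptions about effect sizes: with complete data the PS-stratified slope difference is the unadjusted one, and with the dropout tried it was almost the same. For the PS-stratified MMRM the supportable statement is narrower. Week 24 is incompletely adjusted for confounding that acts on rate of decline. Roughly 60-96% remains for slope SD 0.10-0.25 points/week and residual SD 1-2.5 points, and less where confounding runs through baseline ALSFRS-R.

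The simulated biases and rejection rates are illustrations, since the documents state no control pool size, variances or degree of imbalance. The matched analyses, the single-timepoint vital capacity ANCOVA and the survival analyses, which use the strata as stratification factors, are unaffected. The models should be corrected because the label would mislead, but no main analysis depends on them.

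**What to change.** In SAP 4.7.2.4, add PS strata-by-visit (continuous week) to the PS-stratified slope model. In 4.7.2.3, add PS strata-by-visit (categorical visit) to the PS-stratified MMRM, as is already done for baseline value. Carry both changes into the PPS repeats and report the treatment contrasts from these models.

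With five strata the cost is 5 − 1 = 4 extra degrees of freedom in the slope model and 4 × (3 − 1) = 8 in the MMRM, plus short changes to text and code. No new data are needed. Bulbar onset-by-visit is optional. If results from the models as now written have been produced, the stratified slope difference should be described as unadjusted for the PS.

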6.0 STUDY PROCEDURES

Participants may receive up to 24 weeks of weekly infusions per protocol. Some assessments may be collected remotely, via telemedicine, or over the telephone with site staff.

Participants may be screened over and up to a 21-day period prior to treatment initiation. Participants who meet the inclusion criteria and none of the exclusionary criteria may be enrolled into the EAP. Participants may initiate treatment on the same day as the combined Screening/Baseline Visit, provided consent was obtained and all inclusion and exclusion criteria have been satisfied and eligibility has been confirmed by the investigator prior to treatment initiation.

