4.1.1 Definitions, Derivations and Classifications

Definition of Baseline

The baseline value for all endpoints (i.e., laboratory parameters and vital signs) will be the last available value prior to the first dose of study treatment in Trehalose group, and the date of first study visit in historical control group.

Assessments taken on the same day as study treatment will be assumed to be before study treatment unless indicated to be obtained post-study treatment.

Definition of Day 1

Study Day 1 is defined as the first day of study treatment in Trehalose group, and the date of first study visit in historical control group. This will also be considered the reference start date.

Definition of Study Day

Study Day will be computed as follows:

- Study Day = (Date of event – Date of study day 1) + 1 if the date of the event is on or after the date of study day 1.
- Study Day = (Date of event – Date of study day 1) if the date of the event is prior to the date of the study day 1.

Derivations Involving Dates

The number of days between two dates, the date of interest and the reference date, will be calculated as (Date of event – Reference date) + 1 when the event date is on or after the reference date; or, as (Reference date – Date of event) + 1 when the event date is before the reference date. The resulting value is then converted to years, months, or weeks, as appropriate. Partial dates will be imputed before calculating the number of days (See Appendix 2 for partial or unknown date imputation rules).

Common Calculations

Change from baseline (CHG) will be calculated as:

$$\text{Change from baseline} = \text{Actual (observed) value at post baseline visit} - \text{baseline value}$$

Percent change from baseline (PCHG) will be calculated as:

$$\text{Percent change from baseline (\%)} = 100 * (\text{Change from baseline at post baseline visit} / \text{Baseline value})$$

If baseline is not available, the change from baseline and percent change from baseline will not be calculated and will remain missing.

Demographics

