4.1.2 Windowing, Unscheduled Visits and Repeat Test Results

All assessments collected at scheduled and unscheduled visits will be included in the by-participant data listings.

For Safety endpoints, the data will be analyzed according to the nominal visits except Baseline which is defined as last available value prior to the first dose of study treatment. The results collected at scheduled visits per

protocol will be included in the by-visit summary tables. For laboratory data analysis at the scheduled visits, central-laboratory values will (preferentially) be selected for a given visit; however, if there is no non-missing central-laboratory value available and there is a non-missing local-laboratory value collected at the visit, then a local-laboratory value will be used.

In addition, for Safety endpoints of laboratory data, vital signs and C-SSRS assessments, the last assessment during the post-baseline period will also be summarized using the analysis visit name “End of Treatment Period”, which is defined as the last measurement from all post-baseline visits including the unscheduled visits and early termination visit.

For Efficacy and Biomarker endpoints, the protocol defined visit windowing in Table 3 will be used to window the unscheduled visits or early termination visit to scheduled visit when it doesn’t exist. If unscheduled visits or early termination assessments fall in the same window, then select the assessment closest to the target assessment day. If there are two assessments that fall into a visit window and are equidistant from the target assessment day, then the later assessment will be selected.

Table 3 Analysis Visit Windows for Efficacy (ALSF-R, SVC, ALSAQ-40) and Biomarker

Analysis Visit	Nominal Day	Lower Limit	Upper Limit
Baseline	1	None	Time of first dose of study treatment
Week 3	22	19	25
Week 12	85	78	92
Week 24	169	155	183

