4.2.1 Eligible Historical Control Analysis Set

The eligible historical control analysis set will be constructed from the available databases relating to clinical outcomes in ALS consisting of previous ALS clinical research study participants who:

- met major eligibility criteria from this EAP study if related information was collected in historical database, including:
 - Inclusion criteria 2: Age 18 years or older.
 - Exclusion criteria 2: Screening glucose ≥ 140 mg/dl
 - Exclusion criteria 6: Screening body weight > 144 kilograms
- and had known mortality information
- and had baseline and at least one post-baseline ALSFRS-R total scores recorded
- and/or had baseline and at least one post-baseline measurements of Vital Capacity (VC) including the collected SVC or Forced Vital Capability (FVC)

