4.8 Other Analyses

4.8.1 Biomarker Analyses

A descriptive analysis of change in NfL levels will be performed at Baseline and Week 24 for FAS by EAP study treatment groups.

In addition, the NfL levels will be performed using a general linear mixed effects model to compare the rate of decrease (ie, slope) of NfL levels over the 24-week treatment period for FAS. The model will fit a random intercept for each participant and will include fixed effects for treatment group, bulbar onset, visit, and treatment by visit interaction. An unstructured covariance structure will be used to model the within-participant errors. Visit will be expressed in months (using actual study days / 30.4375) as a continuous variable including the baseline visit and all post-baseline visits. Missing values will not be imputed.

Estimates of the slope will be presented by treatment group along with corresponding 95% CIs.

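### The ALSFRS-R slope comparison with historical controls uses the EAP's nominal weeks, with no rule for placing control visits and a Week 0 that can precede Day 1 in the EAP group only

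*SAP*

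**What the plan says.** - **Purpose of the model.** SAP 4.7.2.4 fits a random intercept and slope per participant to "compare the rate of decrease (ie, slope) of total ALSFRS-R scores over the 24-week treatment period" between trehalose participants and historical controls, once for the matched and once for the stratified comparison, in both FAS and PPS.
- **Time variable.** "Visit will be expressed in weeks as a continuous variable and will include all scheduled visits including baseline as Week 0". The section then lists Weeks 0, 3, 12 and 24.
- **Windows.** SAP 4.1.2 says "the protocol defined visit windowing in Table 3 will be used to window the unscheduled visits or early termination visit to scheduled visit". Table 3 gives Days 19–25, 78–92 and 155–183. Nothing there mentions control visits.
- **Controls.** SAP 4.2.1 admits a control who "had baseline and at least one post-baseline ALSFRS-R total scores recorded", with no limit on when the later score was taken. (Vital capacity data are an and/or alternative.) The SAP version history names Answer ALS as the chosen database. Its visit schedule appears nowhere in the two documents.
- **Baseline.** SAP 4.1.1 sets it as "the last available value prior to the first dose of study treatment in Trehalose group, and the date of first study visit in historical control". Day 1 is the first dose in the EAP and the first study visit in controls.
- **Screening period.** Protocol 6.0: "Participants may be screened over and up to a 21-day period prior to treatment initiation". Protocol 5.0 makes same-day Screening and Baseline the default and allows a split.
- **NfL model.** SAP 4.8.1: "Visit will be expressed in months (using actual study days / 30.4375) as a continuous variable".

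**The concern.** A nominal week is a fair stand-in for elapsed time only when everyone follows the same schedule from the same origin. Neither condition is secured here.

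First, the SAP does not say which control score counts as Week 3, 12 or 24. Either Table 3 is extended to controls and dated scores between windows are dropped, or the mapping is chosen after the control data are in hand. The main repeated-measures model in SAP 4.7.2.2 uses the same scheduled visits, so it has the same gap.

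Second, Week 0 can mean different things in the two groups. In the EAP, Weeks 3, 12 and 24 are counted from first dose, but the Week 0 score may be older than that. In controls the baseline score and Day 1 fall at the same visit. Any decline between an early EAP baseline and first dose is then charged to the 24 treated weeks, in that group only.

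**Working it through.** The documents give no sample size, power or effect size for this comparison, so there is no stated figure of that kind to reproduce.

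**1. Table 3.** The protocol schedule has Days 21 ± 3, 84 ± 7 and 168 ± 14 with first dose as Day 0. The SAP calls first dose Day 1, so add one: 22 ± 3 = 19–25, 85 ± 7 = 78–92, 169 ± 14 = 155–183. Table 3 reproduces exactly.

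**2. Coverage.** The windows hold 7 + 15 + 29 = 51 days, and 51/183 = 28%. This alone does not give the loss, because visits are not spread evenly over days.

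**3. Loss if Table 3 were applied to controls.** The control schedule is unknown, so the visit interval is an assumption. Visits were placed at multiples of the interval after Day 1, with normal scatter of SD 0, 7 or 14 days, rounded to whole days, and one score was kept per window. The denominator is all scores on Days 2–183 (100,000 simulated controls per row and SD).

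| Assumed interval | Scores kept, SD 0 / 7 / 14 days | Controls with no in-window post-baseline score |
|---|---|---|
| Monthly | 20% / 25% / 24% | 0% / 12% / 13% |
| 6 weeks | 50% / 42% / 31% | 0% / 1% / 16% |
| 2 months | 0% / 20% / 25% | 100% / 50% / 45% |
| 12 weeks | 100% / 85% / 60% | 0% / 1% / 18% |
| 3 months | 100% / 66% / 56% | 0% / 25% / 33% |

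Hand check at SD 0: monthly visits fall on Days 31, 62, 92, 123 and 153, and only Day 92 is in a window (1 of 5). Two-monthly visits fall on Days 62 and 123, neither in a window. Twelve-weekly visits fall on Days 85 and 169, both in a window. The Week 3 window is hit by at most 16% of controls (monthly visits) and by essentially none at intervals of 2 months or longer.

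**4. Effect of an early EAP baseline.** Assume linear decline and ordinary least squares on complete data. Coded times are 0, 3, 12, 24, with mean 39/4 = 9.75.

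- Sum of squares: 9.75² + 6.75² + 2.25² + 14.25² = 348.75.
- If the baseline was really L weeks before Day 1, true times are −L, 3, 12, 24. The fitted slope is multiplied by 1 + 9.75 L / 348.75.
- L = 1: 1.028. L = 2: 1.056. L = 3: 1 + 29.25/348.75 = 1.084.
- With only baseline and Week 24, the factor at L = 3 is (168 + 21)/168 = 189/168 = 1.125.
- If 25% or 50% of EAP participants had the full 21-day lag and the rest none, the mean distortion would be 0.25 × 8.4% = 2.1% or 0.5 × 8.4% = 4.2%.

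**5. Nominal coding inside a window.** A Week 24 visit made two weeks early or late but coded 24 changes that slope by 14.25 × 2 / 348.75 = 8.2%, down or up.

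**6. With actual time from the baseline score.** The lag distortion is 0 for any L, and all control scores to Day 183 can be used.

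**The case against.** A reader might infer that control data are lost, or that controls have no visits at these weeks. The documents do not establish either. Table 3 is written for unscheduled and early termination visits, nothing extends it to controls, and the control schedule is not given. With visits close to every 12 weeks or 3 months the loss could be nil. What the text shows is a missing mapping rule.

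A reader might also infer that matched pairs lose their control member. That is not so in the slope model. Week 0 is part of the response and the matched ID is a random effect, so a control with only a baseline score stays in. It adds no information on slope. It would drop out of the change-from-baseline model in SAP 4.7.2.2, which has only post-baseline responses, but even there its partner remains.

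On the lag, 12.5% is a two-point maximum and should not be read as the bias of the planned model. Same-day completion is the default. Even when the visit is split, baseline is the last value before first dose, and nothing assigns the ALSFRS-R to the Screening half. The bias makes EAP decline look steeper, so by itself it cannot produce a false benefit.

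The stakes are also limited. The analysis is supplementary, and SAP Section 2 calls all analyses descriptive, with unadjusted exploratory p-values.

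All of this stands, and it limits the size of the point. It does not supply the missing rule, nor explain why ALSFRS-R time is nominal when NfL time is actual.

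**Conclusion.** The concern holds in a limited form. The slope model imposes the EAP's nominal weeks on controls from another study, and the SAP gives no rule for placing their visits. If Table 3 were used, the share of control scores kept would range from all to none across the schedules assumed above. The true figure cannot be known from the documents.

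The two groups' origins can also differ. At the 21-day maximum an affected EAP participant's slope is 8.4% too steep with four visits. The group effect is smaller in proportion to how often and by how much baselines precede first dose, and it is zero if none do. The 8.4% assumes linear decline, complete data and equal weighting of visits; another covariance structure or missing visits would change it. The direction is against trehalose.

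This deserves correction because a better method is nearly free and a random-slope model does not need common visit times. It does not undermine any confirmatory conclusion, since the plan makes none.

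**What to change.** **SAP 4.7.2.4.** Define time in both groups as actual days from each person's baseline ALSFRS-R assessment, divided by 7. Include every dated ALSFRS-R score up to Day 183, whether or not it falls in a Table 3 window. Report how many matched controls have no post-baseline score in that period. This follows SAP 4.8.1 in principle. That model counts study days from Day 1, whereas this one counts from the baseline score, so that Week 0 has the same meaning in both groups.

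**SAP 4.7.2.2.** State the rule that maps control visits to Weeks 12 and 24, and omit the Week 3 treatment difference if controls have no Week 3 data.

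**Cost.** SAP wording and minor programming. This assumes that the control database holds ALSFRS-R assessment dates, which the documents do not confirm.
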